Following results of the 12-month blinded period, all eligible subjects will switch from Viaskin Milk 500 µg to Viaskin Milk 300 µg for 24 additional months, independently of the duration of previous treatment with Viaskin Milk 500 µg:

- Subjects who will decline to switch to Viaskin Milk 300 µg will be discontinued from the study and an ET visit or an EOS visit will be performed (see [Section 7.2.3](#));
- Subjects who will switch to Viaskin Milk 300 µg will be treated for 24 additional months:
 - Until Visit S1 is performed and the subjects start with Viaskin Milk 300 µg, they will continue to receive Viaskin Milk 500 µg. No DBPCFC should be performed while the subjects are still receiving Viaskin Milk 500 µg.
 - Subjects will then follow a dedicated study flowchart (see [Table 6](#) and [Table 7](#)),
 - Optional DBPCFCs can be performed after 12 and/or 24 months of treatment,

If the decision is made by the Investigator and the subject to perform a DBPCFC, its performance must comply with the standardized methodology defined in [Section 7.3.1.1](#). Standardized milk and placebo food challenge formula and material as well as the Manual of Procedures will be provided to all sites and must be used for conducting the food challenge.

When performed, the results of these food challenge(s) will be documented and reported in the e-CRF.

- The EOS visit will take place 2 weeks after the end of the treatment period.

[figure not shown]
During their participation in the study all subjects will be instructed to remain on a strict cow's milk-free diet with no consumption of dairy products or baked milk products until their final study visit (except during DBPCFC). At the end of participation in the study, the re-introduction of milk products (eg, dairy products or baked milk products) into the subject's diet, or the decision to keep the subject under a strict cow's milk-free diet will be left to the Investigator's discretion.

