All DBPCFCs at Month 12 and forward will be conducted using the same procedures that are described for the screening DBPCFC, with the exception that the dosing will continue beyond the 300 mg dose of cow's milk proteins if there are no objective symptoms (see [Section 7.3.1.1.3](#)) at the 300 mg dose. The challenge must be continued up to the last dose of 3000 mg of cow's milk proteins or until an objective reaction occurs (as defined in [Section 7.3.1.1.3](#)).

For all DBPCFCs at Month 12 and forward, the doses of cow's milk proteins will be 1 mg, 3 mg, 10 mg, 30 mg, 100 mg, 300 mg, 1000 mg, 2000 mg, and 3000 mg administered at 20-minute intervals. The Investigator may use clinical judgment to increase the intervals between doses in case there is a suspicion that an objective reaction may be developing (see [Section 7.3.1.1.3](#)). Very occasionally, the Investigator may use clinical judgment to repeat the same dose (only once) before administration of the next higher dose and only if there is a suspicion that an objective reaction may be developing (see [Section 7.3.1.1.3](#)). The dose and time of administration of each dose (and of a repeated dose when applicable) will be recorded in the eCRF. The subjects

will be kept under observation for an additional 3 hours after the ingestion of the last dose of the challenge formula.

Subjects should undergo both days of the DBPCFC (milk and placebo). However, in exceptional cases, the DBPCFC on the second day of the challenge might not be performed if the subject had a severe anaphylactic reaction during the first day of the challenge, leaving no doubt about the nature of the formula administered, ie, cow's milk. In this rare case and in this case only, the formula will be unblinded to confirm that the subject effectively received the milk formula. A severe anaphylactic reaction would involve a >20% drop of blood pressure, cyanosis or SpO₂<92%, confusion, collapse, loss of consciousness, 3 doses of epinephrine or more (see [Appendix 14.4](#)).

At the end of the second day of the food challenge, the sequence of the 2 formulas (milk or placebo) administered will be unblinded by the appropriate unblinded staff (eg, dieticians, study nurses, pharmacists, pharmacy technicians, licensed medical assistants, or any other qualified site personnel, as delegated by the Investigator) and revealed to the medical staff. The results of the challenge will then be established and recorded in the eCRF.

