7.3.1.1.3 Criteria for Stopping the DBPCFC

The instructions for each of the DBPCFCs during the double-blind period (Screening, Month 12), the Viaskin Milk 500 µg open-label period (Month 24, Month 36 and Month 48) and the Viaskin Milk 300 µg open-label period (12 and 24 months after the switch) are provided below. Further details are provided in the Manual of Procedures for the DBPCFC.

Only clear-cut OBJECTIVE immediate-type symptom(s) requiring treatment will be considered a permissible reason to stop the DBPCFC and to determine the eliciting dose (highest dose given during the challenge) and the CRD of cow's milk. For the open-label treatment period with Viaskin Milk 300 µg, abdominal complaints will also be considered as a criterion for stopping the challenge (see below). The main objective symptoms to expect are as follows (this list is not exhaustive; also refer to [Appendix 14.2](#), OFC Symptom Score Sheets^{21, 22}): local or generalized pruritus, flushing, local or generalized urticaria, hives, swollen lips, swollen tongue, throat tightness, vomiting, diarrhea, dyspnea, rhinorrhea, sneezing, wheezing, conjunctivitis, asthma, drop of the PEF, hypoxia, hypotension, hypotonia, decreased level of consciousness associated with collapse and/or incontinence or other life threatening symptoms.

The stopping rules applying for DBPCFCs performed during the double-blind placebo-controlled period and the open-label treatment period with Viaskin Milk 500 µg were the following:

- There is a >1-point rise in an objective symptom from any category in the OFC Symptom Score Sheets, except only for pruritus, which requires >2-point rise
- There is ≥1-point rise in an objective symptom from ≥2 categories in the OFC Symptom Score Sheets
- There is a 1-point rise in an objective symptom from 1 category in the OFC Symptom Score Sheets, with the following exceptions:
 - Pruritus : 0 to 1 or 0 to 2
 - Urticaria: 0 to 1

- Rash: 0 to 1
- Sneezing/Itching: 0 to 1
- Nasal Congestion: 0 to 1
- Rhinorrhea: 0 to 1
- Laryngeal: 0 to 1 (if explained and not persistent)

The stopping rules applying for DBPCFCs performed during the open-label treatment period with Viaskin Milk 300 µg are the following:

Only 1 out of 5 categories has increased its grading symptom score

≥ 1-point rise (i.e. mild, moderate or severe)	OR	≥ 2-point rise (i.e. moderate or severe)	OR	3-point rise (i.e. severe)

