
 ○ Wheezing ○ Objective Gastrointestinal** ○ Cardiovascular/neurological*** 		
 ○ Urticaria ○ Angioedema ○ Rash 		
 ○ Pruritus ○ Sneezing /Itching ○ Nasal Congestion ○ Rhinorrhea ○ Conjunctivitis ○ Abdominal complaints

2 categories (or more) have increased their grading symptom scores

≥ 1-point rise (i.e. mild, moderate or severe)	AND	≥ 2-point rise (i.e. moderate or severe)

 ○ Urticaria ○ Angioedema ○ Rash ○ Laryngeal* ○ Wheezing ○ Objective Gastrointestinal** ○ Cardiovascular/neurological*** 		
 ○ Pruritus ○ Sneezing/Itching ○ Nasal Congestion ○ Rhinorrhea ○ Conjunctivitis ○ Abdominal complaints

* "Laryngeal" means symptoms due to laryngeal oedema and must be differentiated from another cause of cough like pharyngeal transient irritation or lower respiratory symptoms. Transient laryngeal irritation will not be considered as an objective OFC symptom and will not be considered in the stopping rules.

**For emesis/vomiting, the symptoms may result from two different situations: vomiting/spitting-up during the feeding, resulting from subjective intolerance to the food formula or vomiting/emacsis resulting from a gastrointestinal allergic reaction to the milk allergen, usually delayed from the feeding. Only the second situation will be considered as an objective OFC symptom and will be considered for the stopping rules.

***Cardiovascular symptoms: hypotension or cardiovascular failure directly related to the systemic allergic reaction. They have to be differentiated from similar symptoms related to another cause, such as a dizziness induced by vomiting.

In case of subjective symptoms, eg, mouth pruritus, throat pruritus, nausea, abdominal pain or any other subjective symptoms at a specific dose, deemed significant enough to question whether an objective symptom could occur, the Investigator can, under these conditions, extend the time between the previous dose and the next dose to see how the subject's symptom(s) evolve(s). The same dose can be repeated only once, to check whether the subjective symptom(s) reappear(s) or not and with what intensity, and whether (an) objective symptom(s) now clearly appear(s). If (an) objective

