symptom appear(s), that would be the end of the food challenge. If only (a) subjective symptom(s) still persist(s) with no appearance of an objective symptom, the next highest dose is then given to the subject, and the challenge should continue until the appearance of a clear objective symptom, at which time the challenge will be stopped.

Complete information of all reactions (objective and subjective symptoms) that occurred during the DBPCFC will be reported in the eCRF, along with information about the doses of cow's milk proteins or placebo administered, time of dose administration, first time of appearance of each symptom, severity grades of each symptom, time of appearance of each severity grade, and medication(s)/treatment(s) given to the subject to treat these symptoms.

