8.1.6.1 Primary Efficacy Endpoint and Analysis

The primary efficacy endpoint will be the percentage (%) of subjects who are treatment responders after 12 months of EPIT treatment.

A treatment responder is defined as a subject who meets at least one of the following criteria:

- A \geq 10-fold increase in the CRD of cow's milk proteins at the Month 12 DBPCFC as compared to baseline value and reaching at least 144 mg of cow's milk proteins (approximately 4.5 mL of milk).
- A CRD of cow's milk proteins \geq 1444 mg (approximately 45 mL of milk) at the Month 12 DBPCFC.

The CRD of cow's milk proteins is entered directly in CRF by the sites and is calculated as the sum of all doses of cow's milk proteins given during the challenge, including repeat doses if applicable, and exact quantity of the last dose given (if not given in totality).

The percentage of subjects who are treatment responders after 12 months of EPIT treatment will be calculated on the ITT population using missing = failure imputation method (ie, subjects with missing observation at Month 12 will be considered as non-responders).

The number and percentage of responders will be summarized overall and by age group, for each pooled dose level (Part A and Part B) and placebo group, for the blinded treatment period (Months 0 to 12).

Methods of exact logistic regression will be used to compare the proportion of treatment responders at Month 12 in each dose level to placebo, adjusting for age group, and including the treatment group as fixed effect, for subjects in the ITT population. P-values, odds ratios together with associated 95% Confidence Intervals (95% CI) will be presented.

The primary efficacy endpoint of this study, together with additional exploratory analyses, will assess the dose-response relationship and aim to inform the dose selection for phase 3. Model-based analytical approaches of exploratory dose finding (e.g., MCP-Mod) will be used to evaluate the dose-response relationship and estimate target dose(s).

Further details of the statistical methodology and considerations for the approaches to be used in the analysis will be specified in the SAP.

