2 = Moderate: dyspnea, inspiratory and expiratory wheezing		
3 = Severe: dyspnea, use of accessory muscles, audible wheezing		

IV. GASTROINTESTINAL

	Stopping rules: minimal # of grade increase	
	Alone	Associated
A. Subjective Complaints	+3	+2
0 = Absent		
1 = Mild: itchy mouth/throat, c/o nausea, abdominal pain, no change in activity		
2 = Moderate: frequent c/o nausea or abdominal pain, decreased activity		
3 = Severe: patient in bed; crying, notably distressed		
B. Objective Complaints	+1	+1
0 = Absent		
1 = Mild: 1 episode of emesis* or diarrhea		
2 = Moderate: 2-3 episodes of emesis* or diarrhea or 1 of each		
3 = Severe: >3 episodes of emesis* or diarrhea or 2 of each		

* Emesis to be differentiated from "spitting-up" due to food intolerance while feeding.

V. CARDIOVASCULAR/NEUROLOGIC

	Stopping rules: minimal # of grade increase	
	Alone	Associated
Cardiovascular/neurologic	+1	+1
0 = Normal: heart rate or BP for age/baseline		
1 = Mild: color change, subjective response (weak, dizzy), or tachycardia, mental status change, mild hypotension (weak rapid pulse and/or 10-20% drop in blood pressure from baseline)		
2 = Moderate: drop in blood pressure >20% from baseline, significant change in mental status, light-headedness, feeling of "pending doom"		
3 = Severe: cardiovascular collapse, signs of impaired circulation, unconsciousness, bradycardia, cardiac arrest.		

14.3 Quality of Life Questionnaire Forms**14.3.1 Food Allergy Quality of Life Questionnaire-Child Form (FAQQLQ-CF)**

FAQLQ-CF

Food Allergy Quality of Life Questionnaire – Child Form (8-12 years)

To cite this questionnaire:

The questions are about the influence of your food allergy on your quality of life. It is important that you fill in the answers yourself. You may ask your parents for help, but they are not allowed to tell you which answer to give. Answer every question by putting an 'x' in the proper box. You may choose from the following answers.

not

barely

a little bit

fairly

quite

very

extremely

How troublesome do you find it, because of your food allergy, that you ...

1 must always watch what you eat?	
2 can eat fewer things?	

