8.2.1.2 OL-300 Analyses

Optional food challenge can be performed after 12 months and/or 24 months of open-label treatment with Viaskin Milk 300 μ g. No DBPCFC was performed at the end of 500 μ g period (prior to switch to open-label treatment with Viaskin Milk 300 μ g).

A responder in the OL-300 analyses is defined as a subject who meets at least one of the following criteria:

- A \geq 10-fold increase in the cow's milk proteins CRD at the Month 12 DBPCFC (VS3/VS4) [Month 24 (VS6/VS7)] after switch to Viaskin Milk 300 μ g as compared to baseline value and reaching at least 144 mg of cow's milk proteins
- A CRD of cow's milk proteins \geq 1444 mg at the Month 12 DBPCFC (VS3/VS4) [Month 24 DBPCFC (VS6/VS7)] after switch to Viaskin Milk 300 μ g

Two types of analyses will be performed, considering different timepoints as baseline:

1. Considering the CRD determined by screening DBPCFC as baseline CRD.
2. Considering the CRD determined by the DBPCFC which was conducted prior to the subject receiving any active treatment as baseline CRD. This refers to Month 12 DBPCFC for subjects randomized to the placebo treatment arm and to screening DBPCFC for subjects randomized to any active treatment arm.

This document is confidential

Statistical Analysis Plan

Both types of responders will be summarized overall and in each age-group, in total and by initial randomized treatment group (placebo/dose level/overall active) in the OLS-300.

For the calculation of rates and percentages, only the subjects with DBPCFC at the respective baseline and at Month 12 (VS3/VS4) [Month 24 (VS6/VS7)] after switch will be used.

8.2.2 Cumulative Reactive Dose (CRD) of Cow's Milk Proteins at Months 12 to 48

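### In the 300 µg period, an isolated 3-point abdominal complaint meets the stopping table, yet the paragraph after the table, read literally, allows a repeat dose or a larger dose.

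*Protocol*

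**What the plan says.** Protocol Section 7.3.1.1.3 opens by saying that its instructions cover every DBPCFC, including those 12 and 24 months after the switch to 300 µg. It starts from an objective-only principle and then makes an exception for the 300 µg period: "abdominal complaints will also be considered as a criterion for stopping the challenge". The 300 µg table puts abdominal complaints among the items that stop the challenge alone at a 3-point rise, separately from objective gastrointestinal signs. Appendix 14.2 row IV.A, headed as subjective complaints, prints +3 for the symptom alone and describes that grade as "3 = Severe: patient in bed; crying, notably distressed".

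After the table and its footnotes comes a paragraph that begins "In case of subjective symptoms, eg, mouth pruritus, throat pruritus, nausea, abdominal pain or any other subjective symptoms at a specific dose". It is confined to symptoms significant enough to make one ask whether an objective symptom might follow. The Investigator may lengthen the interval and may repeat the dose once. If only a subjective symptom persists "with no appearance of an objective symptom, the next highest dose is then given to the subject, and the challenge should continue", until a clear objective symptom appears.

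Section 7.3.1.1.2 continues dosing to 3000 mg "or until an objective reaction occurs (as defined in" Section 7.3.1.1.3). For the optional 300 µg challenge, Section 3.1.4 says "its performance must comply with the standardized methodology defined in" Section 7.3.1.1, and it also makes the Manual of Procedures mandatory.

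The CRD is the sum of all doses given, "including repeat doses if applicable, and exact quantity of the last dose given (if not given in totality") (Protocol 8.1.6.1). SAP 8.2.1.2 defines OL-300 responders against two baselines: the screening CRD, and the last CRD before any active treatment. Of the second it says: "This refers to Month 12 DBPCFC for subjects randomized to the placebo treatment arm".

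**The concern.** One clinical picture, a severe abdominal complaint with no objective sign, falls under two instructions in the same section. The table ends the challenge. The paragraph permits a repeat and then leads to the next dose. Nothing says which prevails.

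The main stake is safety: a milk-allergic child in bed, crying and distressed, could be given more milk protein after meeting the rule meant to stop the challenge. The second stake is the data. Every extra milligram enters the CRD, so two sites facing the same child could record different CRDs and different responder status.

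**Working it through.** The plan gives no figure on this point to reproduce. The check sets the texts side by side and then follows the dose arithmetic.

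**Step 1: the instructions.** Take a child on 300 µg whose only change is an abdominal complaint rising from 0 to 3, at a dose below 3000 mg.

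- 300 µg table (7.3.1.1.3): one category, 3-point rise. Stop.
- Row IV.A (Appendix 14.2): +3 alone. Stop.
- Subjective-symptom paragraph (7.3.1.1.3): abdominal pain is named, and a grade 3 complaint is serious enough to fall within its condition. Waiting or one repeat is optional. If the complaint persists with nothing objective, the next dose follows.
- Section 7.3.1.1.2: continue until an objective reaction. Because it defers to 7.3.1.1.3, it adds no separate conflict and only needs aligning.

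The conflict is confined to the isolated branch. In the two-category branch another listed sign must be present. SAP 8.2.5.1 classes those signs as objective, so the paragraph would end the challenge too.

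**Step 2: size of the next dose.** The doses are 1, 3, 10, 30, 100, 300, 1000, 2000 and 3000 mg (7.3.1.1.2). The ratios of each dose to the one before are 3.0, 3.3, 3.0, 3.3, 3.0, 3.3, 2.0 and 1.5. The next dose is therefore 1.5 to 3.3 times larger.

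**Step 3: responder status without repeat or partial doses.** The cumulative doses are 1, 4, 14, 44, 144, 444, 1444, 3444 and 6444 mg. Under SAP 8.2.1.2 a responder has (CRD ≥ 10 × baseline and CRD ≥ 144) or CRD ≥ 1444. For baseline B this is CRD ≥ T, with T = min(max(10B, 144), 1444). The step at which one more full dose changes the status is:

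| Baseline B (mg) | T (mg) | CRD if stopped (mg) | CRD after next full dose (mg) |
|---|---|---|---|
| 1, 4 or 14 | 144 | 44 | 144 |
| 44 | 440 | 144 | 444 |
| 144 | 1440 | 444 | 1444 |
| 444 or higher | 1444 | 444 | 1444 |

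Without repeats, screening baselines end at 444 mg. Higher values arise only where Month 12 serves as baseline for placebo-randomized children.

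**Step 4: repeat or partial doses at baseline.** Repeats are allowed at screening (7.3.1.1.1) and count in the CRD, as do partial last doses. Other baselines therefore occur, and a change of status can need much less:

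- Baseline 1 + 1 + 3 + 10 = 15 mg: T = 150. From 144 mg, 150 − 144 = 6 of 300 mg is enough (2%).
- Baseline 1 + 3 + 10 + 10 = 24 mg: T = 240. From 144 mg, 240 − 144 = 96 of 300 mg (32%).
- Baseline 1 + 3 + 10 + 30 + 30 = 74 mg: T = 740. From 444 mg, 740 − 444 = 296 of 1000 mg (29.6%).

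In these three cases a full repeat of the stopping dose is enough by itself: 144 + 100 = 244 mg exceeds 150 and 240, and 444 + 300 = 744 mg exceeds 740.

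**Step 5: stable or improved.** SAP 8.2.2.2 counts any CRD above baseline as improvement. For a child whose CRD at the stopping point equals baseline, any extra amount turns stable into improvement.

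**The case against.** The strongest answer is that the protocol already settles the matter. It states the objective-only principle, makes an express exception for abdominal complaints at 300 µg, and then gives a table headed for that period. Once the table is met the challenge is over, and no next dose remains to be decided. The +3 is printed on the score sheet that Visits S3, S4, S6 and S7 direct staff to use. The paragraph is a watch-and-wait procedure for doubtful symptoms: the next dose comes only if symptoms persist. The Manual of Procedures gives further detail, and challenges are medically supervised.

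Most of this stands as evidence of intent. It does not remove the instruction. The paragraph is itself specific, since it names abdominal pain, and the section says it covers the 300 µg challenges. With the Month 12 challenges complete and challenges on 500 µg discontinued, the optional 300 µg challenges are the only ones it can still govern. Waiting and repeating are discretionary; the next-dose sentence is not worded that way. Section 3.1.4 makes the protocol section itself binding, so an unseen manual is not a full answer.

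A second objection stands in full. Baseline CRD, at screening or Month 12, was measured under objective-only stopping. A reader might infer that continuing past the complaint simply inflates OL-300 efficacy. The documents do not support that: cutting the CRD at the complaint would set it against a baseline obtained under a different rule and push the change downward.

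**Conclusion.** The conflict is real but narrow: an isolated 3-point abdominal complaint, in the optional 300 µg challenges, below the top dose. Read literally, a child who has met the stopping rule could receive a repeat dose, or one 1.5 to 3.3 times larger. That is enough to correct the text on safety grounds. My confidence is medium, because the table is the likely intent and the manual may say so.

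The effect on data is secondary. An extra dose can change an individual child's OL-300 category at the steps shown, but those summaries are descriptive, uncontrolled and drawn from an optional challenge. The documents give no frequency, and it may be zero.

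Three stronger readings go too far. A reader might infer that the protocol flatly orders a larger dose, but the paragraph has a scope condition, an optional wait or repeat, and a persistence requirement. A reader might infer that a change of status needs almost the whole next dose. That is true only for baselines free of repeat and partial doses; otherwise 6 of 300 mg can suffice. A reader might also infer doubt about the Month 12 primary result. Those challenges used the earlier stopping rules, which had no abdominal-complaint criterion, so that result is unaffected.

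**What to change.** 1. Add to the subjective-symptom paragraph of 7.3.1.1.3: *In the 300 µg period this paragraph applies only to subjective symptoms below the table thresholds; a 3-point rise in abdominal complaints ends the challenge and no repeat or further dose is given.*
2. In 7.3.1.1.2, replace "or until an objective reaction occurs (as defined in" Section 7.3.1.1.3) with *or until a stopping rule of Section 7.3.1.1.3 is met*.
3. Optionally, list in the SAP any OL-300 challenge continued past a grade 3 abdominal complaint. The sponsor should first define the row: the table speaks of abdominal complaints, row IV.A also contains itchy mouth and throat, and SAP 8.2.5.1 scores four subjective symptoms separately.

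A sensitivity analysis with CRD truncated at the complaint is not recommended. If one is shown, it needs the caveat that baseline CRD used objective-only stopping. The site-entered CRD stays the main value.

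The cost is two short text changes, a site memo if 300 µg challenges remain to be done, and at most one listing. Section 7.3.1.1.3 already requires doses, dose times, symptom grades and the time of each grade in the eCRF.
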